6.2 Usage of Concurrent/Concomitant Medications

Concomitant medications are any prescription medications or over-the-counter preparations used by the patient within 28 days of initiating study treatment, during study treatment, or until 28 days following study termination. The details of all concurrent medications including vitamins and alternative therapies will be recorded on the case report forms (CRFs). All medications must be reviewed for potential interaction with study drug therapy. All concomitant medications and blood products, as well as supportive interventions (such as analgesic use, paracentesis, etc.) received by patients from screening until the end of study visit will be recorded in CRFs. Because there is a potential for interaction between the study drugs temsirolimus and sorafenib and other concomitantly administered drugs through hepatic metabolism by the cytochrome P450 system (predominantly CYP3A4), P-glycoprotein metabolism, and/or through glucuronidation by UGT1A1 and UGT1A9, the case report form must capture the concurrent use of all other drugs, over-the-counter medications, or alternative therapies. The Study Chair should be alerted if the patient is taking any agent known to affect or with the potential to affect selected P450 isoenzymes or other drug metabolism pathways.

Use of any inducers and strong inhibitors of CYP3A4 is prohibited while undergoing protocol therapy. Use of substrates of CYP3A4, CYP2B6, CYP2C8, and CYP2C9 with a narrow therapeutic range or which are assessed as sensitive by FDA guidelines is also prohibited.(2009) Please refer to Appendices B6-9 for definitions and lists of these agents. Patients who have taken medications that are known to be inducers or strong inhibitors of CYP3A4 within 28 days before registration will be excluded from study.

Substrates of CYP3A4, CYP2D6, CYP2C8, and CYP2C9 with a narrow therapeutic range or assessed as sensitive by FDA guidelines must not have been taken within 5 half-lives of the specific drug in question at the time of start of study. Medications which are weak to moderate inhibitors of CYP3A4 enzymes must be reviewed by the Study Chair or Investigational Pharmacist for approval before concomitant use. Inhibitors or inducers of P-gp, substrates of UGT1A1 and UGT1A9, and other substrates of CYP3A4, CYP2B6, CYP2C8, and CYP2C9 should be avoided or used with caution. Selected medications and substances known or with the potential to interact with or be metabolized by relevant cytochrome P450 isoenzymes (CYP3A4, CYP2B6, CYP2C8, CYP2C9), P-glycoprotein pathway, and/or UGT1A1 and UGT1A9 glucuronidation are provided in Appendices 6-9. If the investigator is unsure of potential for drug-drug interaction, the Investigational Pharmacist will be consulted. For the most up to date table of cytochrome P450-related drug interactions, please refer to the Indiana University drug interaction table at the following website:

<http://medicine.iupui.edu/clinpharm/ddis/ClinicalTable.asp>

6.3 Reasons to Withdraw a Subject

The Investigator will withdraw a patient whenever continued participation is no longer in the patient's best interests. Reasons for withdrawing a patient include, but are not limited to, disease progression, the occurrence of an adverse event or a concurrent illness, a patient's request to end participation, or simply significant uncertainty on the part of the Investigator that continued participation is prudent. There may also be administrative reasons to terminate participation, such as concern about a patient's compliance with the prescribed treatment regimen.

6.4 Stopping Rules

No interim assessment for primary endpoint is planned, but there will be a planned interim safety analysis by the UCSF Data and Safety Monitoring Committee after the first 30% of the planned study participants (8 patients) have enrolled and completed at least one cycle of protocol therapy or been removed for toxicity. Study accrual will not be interrupted for the early

safety assessment. The proportion of patients with treatment-related adverse events of grade 3 or higher and/or an unacceptable toxicity event (with exceptions defined below) will be summarized with 90% two-sided exact confidence intervals. Each confidence interval will be no wider than ± 0.17 . If the lower confidence bound (LCB) exceeds 0.17, adverse events will be evaluated and a decision will be made whether to amend the protocol or close the study.

If the true rate of treatment-related toxicity is 25%, the probability that 3 or more patients will have adverse events of grade 3 or greater is 32%. A summary of probabilities for a range of true toxicity rates is shown below. If 3 or more patients among the first 8 experience an eligible grade 3 or higher and/or unacceptable toxicity event, a decision will be made whether to amend the study or close the study due to toxicity.

True Toxicity Rate	Probability 3 or more of 8 patients experience AEs of grade 3 or greater	Probability 2 or more of 8 patients experience AEs of grade 3 or greater	Probability 1 or more of 8 patients experience AEs of grade 3 or greater
10%	3.8%	18.7%	57%
20%	20.3%	50.0%	83%
25%	32.0%	63.3%	89%
30%	44.8%	74.5%	94%

Exceptions of toxicity which will not be included for interim safety analyses are:

- Asymptomatic Grade 3 toxicity in laboratory values despite optimal supportive care (such as hydration or electrolyte repletion) must be treatment-related, clinically relevant*, and represent a change of ≥ 2 grades from baseline. Grade 3 hypertriglyceridemia is excluded if peak serum triglycerides are < 1500 mg/dL and recover to < 300 mg/dL with optimal medical management by the start of Cycle 2. Asymptomatic Grade 3 hypophosphatemia is also excluded.
- Grade 3 hypertension that resolves to $< 140/90$ within 14 days of adjustment or addition of oral blood pressure medication(s) is also excluded. Hypertension that requires hospitalization or intravenous medication for control will be considered unacceptable toxicity.
- Grade 3 ascites, encephalopathy, or other toxicities associated with chronic liver disease must be ≥ 2 grades greater than baseline to be considered a DLT.
- Fatigue is excluded.
- Toxicity attributed to hepatocellular carcinoma is excluded.

*Clinically relevant is defined as toxicity which places the patient at risk for morbidity by the judgment of the treating investigator.

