Study Drug	Premedication; precautions	Dose	Route	Schedule	Cycle Length
Temsirolimus	Premedicate with diphenhydramine 30 minutes prior to temsirolimus infusion; monitor every 15 minutes during infusion; administer with in-line filter	10 mg	IV	Weekly(± 3 days)	4 weeks (28 days)
Sorafenib	Take on empty stomach or with low fat meal	200 mg	Oral	BID	

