- **Antihyperlipidemic Agents:** Patients who develop serum cholesterol > 350 mg/dL and/or triglycerides > 300 mg/dL while on therapy will require medication (assuming no contraindications and with standard precautions as appropriate for the class of agents chosen) and/or dietary modifications at the discretion of the treating investigator. Pravastatin or rosuvastatin is recommended if LDL and/or total cholesterol are elevated, with or without

elevated triglycerides, because these agents are not CYP 3A4 substrates. Atorvastatin may also be used with caution. If triglycerides alone are elevated, fenofibrate may be considered.

- **Antihypertensive Agents:** Patients who develop blood pressures > 140/90 mm Hg on at least 2 occasions should be managed with oral antihypertensives including amlodipine, hydrochlorothiazide, or metoprolol by their treating physician. Angiotensin converting enzyme (ACE) inhibitors should be used with caution due to increased risk for angioedema when used in combination with temsirolimus. Use of angiotensin receptor blockers (ARB) which are CYP2C9 substrates as well as inhibitors should be avoided or used with caution due to potential for interaction with sorafenib which is also a CYP2C9 inhibitor. Blood pressure and any relevant laboratory parameters should be rechecked within 7 days of starting a new medication.
- **Diuretics:** Diuretics such as furosemide may be used for the management of periorbital or lower extremity edema or ascites at the discretion of the treating physician. Severe episodes of edema, such as congestive heart failure, pleural effusion, ascites, pericardial effusion, or pulmonary edema may require additional measures such as percutaneous drainage or hospitalization.
- **Electrolyte Supplementation:** Electrolytes should be repleted according to standard institutional protocols. Specific recommendations for prevention and management of **hypophosphatemia**, a common side effect of temsirolimus, are provided below:

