6.1 Schedule of Procedures and Observations

The study-specific assessments are detailed in this section and outlined in *Table 6.1 Schedule of Study Procedures and Assessments*. For more details on the study procedures, please refer to Study Laboratory and Procedures Manual.

Screening assessments must be performed within 28 days prior to the first dose of investigational product.

All on-study visit procedures are allowed a window of ± 7 days unless otherwise noted.

All patients who are consented will be registered in OnCore®, the UCSF Helen Diller Family Comprehensive Cancer Center Clinical Trial Management System (CTMS). The system is password protected and meets HIPAA requirements. A written, signed, informed consent form (ICF) and a Health Insurance Portability and Accountability Act (HIPAA) authorization must be obtained before any study-specific assessments are initiated. A copy of the signed ICF will be given to the subject and a copy will be filed in the medical record. The original will be kept on file with the study records.

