6.1.1.1 Screening Assessments

The Screening procedures and assessments must be completed within 28 days of the Day 1 Visit unless otherwise stated. Any results falling outside of the reference ranges may be repeated at the discretion of the investigator.

- Complete physical examination, including height and weight measurement
- Vital signs, including temperature, blood pressure, heart rate, pain score, and oxygen saturation
- Complete medical history with annotation to include demographics, past medical history, presentation at diagnosis, prior biopsy pathologic results (if any), prior radiologic assessments, prior therapies (including surgery, radiation, or local therapies such as chemoembolization), response to prior therapies, and review of systems

- Documentation of disease status including CT chest (with or without contrast) and contrast-enhanced CT and/or MRI abdomen/pelvis, preferably multiphasic
- ECOG Performance Status – see Appendix 1
- Child-Pugh class assessment – see Appendix 2
- BCLC and CLIP stage – see Appendix 3
- History of prior treatments and any residual toxicity relating to prior treatment
- Baseline medications taken within 28 days of Day 1
- Obtain archival tumor specimens (prefer at least 1 tumor block and/or at least 10 unstained slides plus 1 H&E slide) and pathology report (locally-obtained pathology report is acceptable at start of study) to confirm diagnosis of HCC, and for specimen banking of left-over frozen or fixed tumor specimens from all enrolled patients; patients may start study prior to obtaining the archival specimen(s) provided the pathology report has been reviewed and filed in study records
- Screening laboratory parameters: CBC w/ Diff, complete metabolic panel (electrolytes, BUN, creatinine, glucose, calcium, magnesium, phosphorus, total bilirubin, alkaline phosphatase, albumin, AST, and ALT), PT/INR, fasting blood glucose, hemoglobin A1c, fasting total cholesterol and triglycerides; hepatitis B and C serologies (HBsAb, HBsAg, HBcAb total and IgM; HCV Ab) (hepatitis B and C serologies may be performed >28 days from Day 1)
- Measurement of hepatitis B viral load (HBV DNA quantitative by PCR) if HBsAg, HBcAb total, and/or HBcAb IgM is/are positive (within 28 days of Day 1)

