6.1.2 Treatment Period

6.1.2.1 Study Procedures – Cycle 1

Days 1, 8, 15, and 22 (within 7 days)

- Complete physical examination, including height and weight measurement
- Vital signs, including temperature, blood pressure, heart rate, pain score, and oxygen saturation
- Evaluation of clinical response or deterioration
- Evaluation of adverse events
- Concomitant medications

- Safety laboratory assessments: CBC w/ Diff, complete metabolic panel (electrolytes, BUN, creatinine, glucose, calcium, magnesium, phosphorus, total bilirubin, direct bilirubin, alkaline phosphatase, albumin, AST, and ALT), INR
- Serum AFP tumor marker (Day 1 only)
- Blood specimen collection for CTC testing (Day 1 only)
- Banking of blood specimens for possible future correlative studies (Day 1 and 8 only) (See Study Laboratory and Procedures Manual)

6.1.2.2 Study Procedures – Day 1 of Cycles 2 and beyond (within 7 days)

- Complete physical examination, including height and weight measurement
- Vital signs, including temperature, blood pressure, heart rate, pain score, and oxygen saturation
- Evaluation of clinical response or deterioration
- Evaluation of adverse events
- Concomitant medications
- ECOG Performance Status
- Safety laboratory assessments: CBC w/ Diff, complete metabolic panel (electrolytes, BUN, creatinine, glucose, calcium, magnesium, phosphorus, total bilirubin, direct bilirubin, alkaline phosphatase, albumin, AST, and ALT), INR
- Fasting total cholesterol, triglycerides, and blood glucose (odd cycles only)
- Hepatitis B viral DNA quantitative in patients with positive hepatitis B viral load at baseline and/or positive HBsAg, HBcAb total, and/or HBcAb IgM (odd cycles only or more frequently at investigator's discretion).
- Imaging with CT chest (with or without contrast) plus triphasic CT abdomen and pelvis with intravenous contrast or triphasic gadolinium-enhanced MRI abdomen/pelvis to assess sites of known tumor using RECIST 1.1 measurements and to monitor for lung toxicity (odd cycles only, every 8 weeks \pm 7 days, starting Cycle 3, Day 1)

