* Patients will be followed every 3-6 months for up to 5 years after study discontinuation or until death, at standard-of-care clinic visits with treating investigator or by telephone calls from treating investigator or a designated study coordinator (± 3 months)

¹ May start study prior to obtaining specimens if pathology report is available

² Confirmation of antiviral therapy with an appropriate antiviral agent for HBV is required in patients with positive hepatitis B surface antigen, HBcAb IgM, and/or viral load

³ Sorafenib will be taken orally twice daily at starting dose with modifications per Section 5.2.3

⁴ Weight and vital signs on Days 8, 15, 22 of Cycle 2 and future cycles

⁵ Disease assessment including Child-Pugh, BCLC, and CLIP scores

⁶ Evaluation of clinical response or deterioration at Follow-Up Visit: overall survival will be measured from time of first dose of therapy to date of death, evaluation of any residual symptomatic adverse events (if applicable), other anti-cancer therapies

⁷ Complete metabolic panel (electrolytes, BUN, creatinine, glucose, calcium, magnesium, phosphorus, total and direct bilirubin, alkaline phosphatase, albumin, AST, and ALT)

⁸ Prothrombin time/ international normalized ratio (PT/INR)

⁹ Hepatitis B viral DNA quantitative in patients with positive hepatitis B viral load at baseline (Screening) and/or positive HBsAg, HBcAb total, and/or HBcAb IgM (odd cycles only or more frequently at investigator's discretion), and end of treatment if not measured within 4 weeks prior.

¹⁰ Screening and Day 1 of odd cycles only (Cycle 3, 5, 7, etc.)

¹¹ Initiate standing phosphate repletion for patients with baseline ≥ Grade 2 hypophosphatemia; adjust dosage as clinically indicated at each visit

¹² CTC on Day 1 of Cycles 1, 2 & 3 only. See Study Laboratory and Procedures Manual for instructions

¹³ Banking blood samples on Cycle 1 Day 1, Cycle 1 Day 8, and Cycle 3 Day 1, and at End of Treatment (if not done within 4 wks). See Study Laboratory and Procedures Manual for instructions

¹⁴ Odd cycles only, every 8 weeks ± 7 days, starting Cycle 3, Day 1

¹⁵ If not done within 8 weeks, imaging with CT chest (with or without contrast) plus triphasic CT abdomen and pelvis with intravenous contrast or triphasic gadolinium-enhanced MRI abdomen/pelvis

¹⁶ May use values from >28 days from registration

¹⁷ Temsirolimus infusion may be performed within ± 3 days

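### The hypertriglyceridemia exclusion in the interim safety rule expires at the start of Cycle 2, but no on-treatment triglyceride test is scheduled before Cycle 3 Day 1

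*Combined protocol and SAP*

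**What the plan says.** Section 6.4 (repeated by reference in 9.3) sets an interim safety look once eight patients have completed a cycle or come off for toxicity. Three or more patients with a countable event prompt a decision to amend or close. Among the exceptions, Grade 3 hypertriglyceridemia is not counted if the peak is under 1500 mg/dL and values "recover to < 300 mg/dL with optimal medical management by the start of Cycle 2".

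The schedule of lipid tests is as follows:

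- Screening (6.1.1.1) includes "fasting total cholesterol and triglycerides".
- The Cycle 1 list for Days 1, 8, 15 and 22 (6.1.2.1) has no lipid test.
- From Cycle 2 on (6.1.2.2), the Day 1 list has "Fasting total cholesterol, triglycerides, and blood glucose (odd cycles only").
- Table 6.1 footnote 10 gives the same timing: "Screening and Day 1 of odd cycles only (Cycle 3, 5, 7, etc".).
- The chemistry panel drawn weekly (Table 6.1 footnote 7) is "Complete metabolic panel (electrolytes, BUN, creatinine, glucose, calcium, magnesium, phosphorus, total and direct bilirubin, alkaline phosphatase, albumin, AST, and ALT"), which has no triglycerides.

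Two other provisions also need a triglyceride value. In 5.3.1, patients whose "triglycerides > 300 mg/dL while on therapy will require medication"; that sentence goes on to allow diet as well or instead, as the investigator sees fit. The hyperlipidemia row of 5.2.3 calls for holding and then reducing temsirolimus at Grade 3 or 4, with weekly rechecks meanwhile.

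**The concern.** The exclusion has two laboratory conditions, a peak and a recovery by a date. Both refer to a period in which the calendar contains no measurement of the analyte. The neighbouring exclusions for blood pressure and phosphate do not have this problem, because both are measured weekly.

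The protocol itself expects the toxicity. Section 4.1.1 says temsirolimus is likely to raise triglycerides and reports that 83% of patients in the renal-cancer phase 3 trial had at least one elevated value. Section 1.2.2.2 lists hypertriglyceridemia among the dose-limiting toxicities of the same two drugs in melanoma, where the maximum tolerated dose was higher than the dose used here.

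At stake are the consistency with which one type of event enters the interim count, and the time at which a rise first becomes known to the treating investigator.

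**Working it through.** **The plan's own figures.** The trigger probabilities in 6.4 come from P(X ≥ 3) = 1 − Σ C(8,x) pˣ(1−p)⁸⁻ˣ, summed over x = 0, 1, 2. At p = 0.25 this is 1 − (0.1001 + 0.2670 + 0.3115) = 0.3215, against a stated 32.0%. At 10%, 20% and 30% it gives 3.8%, 20.3% and 44.8%, as stated. The other two columns agree within one percentage point. The table is sound, and nothing below changes it.

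**Inputs for the calendar.** Table 5.1 gives a cycle length of "4 weeks (28 days"). Section 6.1 says: "All on-study visit procedures are allowed a window of ± 7 days unless otherwise noted". Section 5.2.3 treats held doses as omitted, so a hold does not shift the cycle calendar.

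**Day counts, with first dose as day 1.**

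| Visit | Nominal day | Window | Triglycerides scheduled |
|---|---|---|---|
| Cycle 2 Day 1 (deadline) | 1 + 28 = 29 | 22 to 36 | No |
| Cycle 3 Day 1 | 1 + 56 = 57 | 50 to 64 | Yes, first on treatment |

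- Nominal gap: 57 − 29 = 28 days.
- Shortest gap: 50 − 36 = 14 days.

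No use of the windows brings a scheduled value to the deadline. After the first dose, chemistry is drawn four times up to and including Cycle 2 Day 1 (Cycle 1 Days 8, 15 and 22, then Cycle 2 Day 1). It is drawn seven times before Cycle 3 Day 1. None of these draws includes triglycerides.

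**What happens to each kind of Grade 3 rise if only scheduled tests are done.**

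1. Peak below 1500 mg/dL, recovered before Cycle 2: unseen and not counted, which is what the exclusion intends.
2. First seen at Cycle 3 Day 1: recovery by the deadline cannot be documented, so the exclusion cannot apply. The event counts by default, subject to the general filter in 6.4 for asymptomatic laboratory values (related to treatment, a risk for morbidity in the investigator's judgment, at least two grades above baseline).
3. Peak of 1500 mg/dL or more that has fallen by Cycle 3 Day 1: missed.
4. Still raised at the start of Cycle 2 but cleared before Cycle 3: missed.
5. Patient reviewed, or off study, before Cycle 3 Day 1: no scheduled value exists. The look needs only one completed cycle, and the end-of-treatment list in 6.1.4 has no lipids.

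The schedule therefore gives the intended answer in case 1. It cannot support the exclusion in case 2 and loses the event in cases 3 and 4. In case 5 it supplies no information.

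**The case against.** The strongest reply is that the missing test rarely changes what the rule does. The exclusion exists to drop transient rises, and a transient rise that nobody sees is dropped. A persistent rise is found at Cycle 3 Day 1 and, having missed the deadline, is not excluded. If an unscheduled test finds a Grade 3 value earlier, 5.2.3 directs weekly rechecks, so recovery can be documented. Section 4.1.1 also advises testing during treatment. This largely stands and keeps the point minor. It does not cover cases 3 to 5 above. The weekly recheck begins only after detection, and the advice in 4.1.1 carries no date.

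A reader might infer that mandatory lipid treatment and a mandatory drug hold are being missed. The documents do not support that. Section 5.3.1 permits dietary change alone at the investigator's discretion. The hold in 5.2.3 applies despite optimal supportive care, and 5.3 requires dose modification for an asymptomatic laboratory change only if it is related to treatment, clinically relevant and at least two grades from baseline. What the gap does is delay the finding on which those judgments rest.

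Other mitigation is also real. Inclusion criterion 13 requires triglycerides under 300 mg/dL at baseline, and 6.1.1 asks for hyperlipidemia to be optimized before therapy. The predecessor HCC trial's list of the most common Grade 3 or higher related toxicities, which runs down to 10%, does not include hypertriglyceridemia (1.2.3.1). That is not a rate, but it is the closest evidence available.

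**Conclusion.** The mismatch holds. A laboratory-defined condition of the safety rule, and first detection of a toxicity the protocol calls likely, have no scheduled measurement for about eight weeks of weekly dosing. The first scheduled on-treatment value comes nominally 28 days after the deadline, and at least 14. These counts rest only on the 28-day cycle and the ±7-day window.

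A reader might go further and infer that the rule is unworkable or that the 3-of-8 trigger is materially distorted. Neither follows. Unscheduled tests are allowed, a Grade 3 value without documented recovery has a default handling, and the trigger leads to a decision rather than an automatic stop. The documents give no rate of countable triglyceride events for this combination in HCC, so any change in the trigger probability would rest on assumed rates and timing. Given the eligibility limit and the clinical-relevance filter, it is probably small. The primary endpoint, sample size and power are not affected. Severity: minor.

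**What to change.** Add fasting triglycerides and cholesterol to one existing Cycle 1 draw, for example Day 15, and to Cycle 2 Day 1. Amend 6.1.2 and Table 6.1 footnote 10 to match. The Day 15 value gives a scheduled chance of detection during Cycle 1, and the Cycle 2 Day 1 value falls at the deadline itself. Two samples will not capture every true peak, but the exclusion could then be applied to scheduled observations.

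The cost is a short protocol amendment, one or two extra assays per patient at visits where blood is already drawn, and fasting for those visits. The timing of the interim look and the probabilities tabulated in 6.4 and 9.3 stay as they are.
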